6.2.2 Subject Disposition

The number (percentage) of enrolled and treated subjects will be summarized as well as subjects who discontinued single drug and subjects who discontinued the combination treatment and reasons for discontinuation. Survival status at the last follow-up visit before data cutoff date will be summarized as well. In addition, the number (percentage) of subjects who remain in each phase at data cutoff date (i.e. treatment phase) will be summarized.

Subject disposition will be summarized by stratum and combined.

6.2.3 Protocol Deviations

Major protocol deviation criteria will be established and subjects with major protocol deviations will be identified and documented before the database lock for the primary analysis of ORR.

Major protocol deviations will be summarized and listed by each category. All protocol deviations identified according to study entry criteria and during treatment will be listed.

6.2.4 Demographic and Other Baseline Characteristics

Demographic and other baseline characteristics for the FAS will be summarized by stratum and combined using descriptive statistics. The derivation of baseline is given in [Section 8](#).

Continuous variables include age, weight, vital signs, height, BMI, and BSA; categorical variables include sex, age group, race, ethnicity, PD-L1 status, pregnancy test status at baseline, ECOG status and enrollment strata. In addition, disease characteristics including time from original breast cancer diagnosis to first study dose, age at original histological/cytological diagnosis, time from MBC diagnosis to first study dose, histology/cytology of the primary tumor, HER-2 status, estrogen (ER) status, progesterone status, lesions baseline, tumor staging at study entry, baseline metastases, and baseline lactate dehydrogenase (LDH) level will be summarized.

6.2.5 Medical History

The number (percentage) of subjects reporting a history of any medical condition, as recorded on the CRF, will be summarized by stratum and overall. A subject data listing of medical and surgical history will be provided. Medical History will be coded using MedDRA (version 22.0) and summaries completed by System Organ Class and Preferred term.

6.2.6 Prior and Concomitant Therapy

All investigator terms (verbatim terms) for medications recorded in the CRF will be coded to an 11-digit code using the World Health Organization Drug Dictionary (WHO DD, version WHODDMAR18_HD_B2) drug codes. The number (percentage) of subjects who took prior or concomitant medications will be summarized on the FAS by Anatomical Therapeutic Chemical (ATC Level 1) class, Pharmacological (ATC Level 3) Class and WHO DD preferred term. Prior medications will be defined as medications that stopped before the first dose of study drug. Concomitant medications will be defined as medications that (1) started before the first dose of study drug and were continuing at the time of the first dose of study drug, or (2) started on or after the date of the first dose of study drug up to 30 days (90 days if given for adverse events) after the subject's last dose. A listing of prior and concomitant medications will be included in the clinical study report for this protocol.

6.2.7 Treatment Compliance

Records of treatment compliance for each subject will be kept during the study. Clinical research associates will review treatment compliance during investigational site visits and at the completion of the study. Treatment compliance will not be summarized since the data will not be entered in the clinical database. However, dose modifications (i.e., reduction/delay/omission) for eribulin will be summarized in [Section 6.6.2](#).

6.3 Data Analysis General Considerations

All efficacy analyses will be summarized in the appropriate analysis set defined in [Section 6.2.1](#) with available data in the clinical database at the data cutoff, by stratum and combined.

6.3.1 Pooling of Centers

Data from all centers will be pooled in the analysis. No adjustment of center effect is planned in the models for the primary, secondary and exploratory endpoints.

6.3.2 Adjustments for Covariates

No adjustments for covariates are planned for primary and secondary analyses in the study. Baseline factors may be used in the model as covariates as supportive analyses for endpoints.

6.3.3 Multiple Comparisons/Multiplicity

No multiplicity adjustments will be made in the exploratory trial. A two-sided alpha of 0.05 will be used in the frequentist tests unless otherwise specified.

6.3.4 Examination of Subgroups

The summaries for primary efficacy endpoint, ORR, and key secondary efficacy endpoints, PFS and OS, will be provided by the following subgroups. Test statistics (i.e. ORR and corresponding 95% CI, median and 95% CI for PFS and OS) for each category will be presented.

- stratification factor (Stratum 1 vs. 2)
- PD-L1 expression (positive vs. negative)
- age group (<50 vs. \geq 50 Years)
- race (White, Non-White)
- baseline Eastern Cooperative Oncology Group (ECOG) performance status (0 vs 1)
- with vs. without bone involvement
- with vs. without liver involvement
- with vs. without lung involvement
- with vs. without brain involvement
- histology type of breast tumor (Ductal Adenocarcinoma vs. Lobular Adenocarcinoma)
- Site of disease (visceral vs. non-visceral only)
- time from original diagnosis to the first study dose (<2 yrs vs. \geq 2 yrs)
- time from metastatic disease to the first study dose (<3 mos vs. \geq 3 mos)
- number of organs involved (\leq 2 vs. >2)
- baseline LDH level (\leq 1.5xULN vs. >1.5 ULN; \leq 2xULN vs. >2ULN)

Additional subgroup analyses may also be conducted after all study data have been examined to better provide an understanding the treatment responses, if deemed necessary.

6.3.5 Handling of Missing Data, Drop-outs, and Outliers

At the time of primary analysis, if death or disease progression is not observed from a subject, corresponding censoring rules for OS and PFS will be followed. They are defined in [Section 8](#).

Potential outlier values will be investigated. They will be analyzed as is in the locked database.

6.3.6 Other Considerations

Not applicable.

6.4 Efficacy Analyses

Approximately 165 evaluable subjects on RP2D will be enrolled in the study, including phase 1b and 2. Subjects enrolled in phase 1b and treated on RP2D level will be pooled with subjects in phase 2 for efficacy analysis. The analysis methods described in Section 6.4 will be applied to the Evaluable Analysis Set (EAS) unless otherwise stated.

6.4.1 Primary Efficacy Analyses

6.4.1.1 ORR in All Subjects

Bayesian predictive probability (PP) design was used in original study design (Yin, 2012). Under original design, in the combined Stratum 1 and 2 subjects, the ORR value per RECIST 1.1 by IIR was assumed to be 0.20 for the historical control (see Table 1 footnote a in protocol amendment 04) and the ORR in this trial was expected to be 0.35. Under protocol amendment 1, approximately 100 evaluable subjects were expected to be enrolled. Bayesian PP was used to monitor the response rate after postbaseline tumor assessments of at least 38 subjects were available. The calculation of PP was based on the goal of claiming superiority of the combination therapy at the end of the study if

$$P(p>0.2|data) \geq 0.95 \quad (1)$$

where p was the response rate of the combination therapy, 0.2 was the response rate of historical control based on single agents pembrolizumab and eribulin in recent trials (Table 1 in Protocol Amendment 4), 0.95 was the prespecified target probability (θ_T), and $P(p>0.2|data)$ is the posterior probability. On the basis of the accumulated data up to time of data monitor in the study, the probabilities of all possible future outcomes that lead to equation (1) at the end of the study would be added in order to obtain the predictive probability as given in (2) below. Therefore, early decision of study termination prior to reaching approximately 100 evaluable subjects was possible for claiming the combination therapy is promising when PP is above a prespecified upper threshold (θ_U) or for claiming futility when PP is below a prespecified lower threshold (θ_L). The upper and lower cutoff probabilities for decision-making, θ_U and θ_L , were set as 0.99 and 0.025. Under the predictive monitoring, the study proceeded as follows:

- If $PP > \theta_U (=0.99)$, stop the study and claim the combination therapy promising
- If $PP < \theta_L (=0.025)$, stop the study and claim the combination therapy not promising
- Otherwise, continue the study until the number of evaluable subjects reaches to 100

The Bayesian stopping boundaries are included in [Appendix 13.1](#).

After completion of enrollment under protocol amendment 1, Bayesian PP is no longer used for continuous monitoring of efficacy and futility as the study will not be stopped early for either efficacy or futility.

Details of Bayesian Approach

Objective Response Rate (p) will be compared to a historical control rate (p_0) of 0.2 via Bayesian posterior probability:

$$\Pr(p > p_0 = 0.2 | \text{data}) \geq \theta_T \quad (1)$$

where a pre-specified target probability (θ_T) is set at 0.95. Without any interim analysis, the trial requires the posterior probability of $p > 0.2$ to be at least 0.95 at the end of the trial in order to demonstrate the superiority of combination therapy over historical control.

Since interim monitoring is implemented in the trial, Bayesian predictive probability (PP) is calculated when there are 38 patients in the Interim Analysis Set (definition in [interim analysis section](#)) to evaluate how likely the trial would complete its full enrollment. Specifically, on the basis of the accumulated data up to the time of data monitor in the trial, PP is calculated by adding the probabilities of all possible future outcomes that lead to equation (1).

Suppose a maximum number of accrued subjects is set as N_{\max} and assume the number of responders X among the current n subjects follows a binomial(n , p) distribution, the posterior distribution $p|x \sim \text{beta}(a+x, b+n-x)$ where $a (=0.2)$ and $b (=0.8)$ are parameters in the prior beta distribution, $p \sim \text{beta}(a, b)$. Let Y be the number of ORR in the potential $m = N_{\max} - n$ future subjects, $Y \sim \text{beta-binomial}(m, a+x, b+n-x)$. When $Y=i$, the posterior distribution of $p|(X=x, Y=i) \sim \text{beta}(a+x+i, b+N_{\max}-x-i)$. The PP can then be calculated as follows,

$$\begin{aligned} \text{PP} &= E\{I[\Pr(p > 0.2 | x, Y)] \geq 0.95 | x\} \\ &= \sum_{i=0}^m \Pr(Y = i | x) I\{\Pr(p > 0.2 | x, Y = i) > 0.95\} \end{aligned} \quad (2)$$

Where $I[A]=1$ if A is true and $I[A]=0$ if A is false. PP characterizes the future trial conclusion given the strength of the currently observed data.

Therefore, early decision of trial termination is possible for efficacy when PP is above a pre-specified upper threshold (θ_U) or for futility when PP is below a pre-specified lower threshold (θ_L). In the current trial, the upper (θ_U) and lower (θ_L) cutoff probabilities for decision making are set as 0.99 and 0.025. Under the predictive monitoring, the trial proceeds as follows:

- If $\text{PP} > \theta_U (=0.99)$, stop the trial and claim the combo promising
- If $\text{PP} < \theta_L (=0.025)$, stop the trial and claim the combo not promising
- Otherwise, continue the trial until the number of evaluable subjects reaches 100

The Bayesian stopping boundaries are included in [Appendix 13.1](#). During the trial, PP will be calculated with updated response information till the boundary is crossed. In case continuous PP monitoring is not conducted because of operational and logistic reasons (e.g. delayed TA assessments and fast enrollment) or it is decided to take the trial to full enrollment even θ_U is crossed in order to gather more efficacy data, posterior probability in equation (1) will be evaluated to determine the efficacy of the combination regimen after the tumor response status has been collected from the last evaluable subjects. That is, to claim efficacy if $\text{Pr}(p>0.2|\text{data}) \geq 0.95$. A two-sided 95% credible interval of ORR based on posterior distribution of p will be constructed to aid the interpretation of the results.

Final Analysis

In the evaluable subjects in Stratum 1 and 2 combined, Bayesian posterior probability in equation (1) will be evaluated to determine the efficacy of the combination regimen after the tumor response status has been collected from the last evaluable subjects. That is, to claim efficacy if $\text{P}(p>0.2|\text{data}) \geq 0.95$. A 2-sided 95% credible interval of ORR in the evaluable subjects will be constructed to aid the interpretation of the results.

Sensitivity Analysis

Sensitivity analyses of ORR for the evaluable subjects in Stratum 1 and 2 combined will be performed using frequentist approach. The hypotheses for the test of ORR are as follows:

$$H_0: p=0.2$$

$$H_1: p>0.2$$

Assuming number of ORR follows a binomial (N_{\max} , p) distribution, the binomial exact test will be used in hypothesis testing. A 2-sided Clopper-Pearson 95% CI will also be constructed.

6.4.1.2 ORR in Stratum 2

Under protocol amendment 3, in Stratum 2 subjects, the hypotheses for ORR per RECIST by IIR are updated to be $H_0: \text{ORR}=0.10$ vs. $H_a: \text{ORR}=0.25$, based on the most recent pembrolizumab monotherapy trial (Table 1 in protocol amendment 4). Therefore, additional subjects will be enrolled to ensure 80 evaluable subjects in Stratum 2 to provide >90% power for the comparison of $H_0: \text{ORR}=0.10$ vs. $H_a: \text{ORR}=0.25$ at 1-sided alpha value of 0.025.

Under Protocol Amendment 4, additional subjects will be enrolled to ensure 100 evaluable subjects in Stratum 2 to obtain more precise estimate of ORR.

Final Analysis

In the evaluable Stratum 2 subjects, a binomial exact test will be used to test the estimated ORR per RECIST 1.1 by IIR versus a historical response rate of 10% at 1-sided alpha value of 0.025. A 2-sided Clopper–Pearson 95% CI of ORR will be constructed for calculating exact binomial intervals.

6.4.2 Secondary Efficacy Analyses

PFS, OS and DOR

Progression-Free Survival (PFS), Overall Survival (OS) and Duration of Response (DOR) will be analyzed using Kaplan-Meier product-limit estimates. Median PFS and OS and the survival rate of PFS (at 6, 9 and 12 months) and OS (at 6, 12 and 18 months), probability of DOR \geq 6, 9 and 12 months will be presented with two-sided 95% CIs, if they can be estimated from the model. Censoring rules and data handling are described for each variable in [Section 8](#) of this SAP.

The probability of PFS, OS and DOR will be plotted over time. The median, first and third quartiles from Kaplan-Meier estimation for PFS, OS and DOR will be provided with 95% CIs if estimable.

Clinical Benefit Rate

A 2-sided Clopper–Pearson 95% CI will be constructed for calculating exact binomial intervals.

6.4.3 Other Efficacy Analyses

The analysis of time to response (TTR) will follow the analysis of PFS. The analysis will be performed in the subjects with confirmed PR/CR by RECIST1.1.

In addition to RECIST1.1 by IIR, tumor assessment data (i.e., ORR, PFS, DOR, and CBR) will be assessed per RECIST1.1 by investigator review and per irRECIST by IIR and investigator review in the sensitivity analysis.

All efficacy analyses will be performed in overall subjects and also for each stratum.

Efficacy outcomes will be further evaluated in the PD-L1 Positive Set. The clinical utility of PD-L1 as a predictive marker in mTNBC subjects who receive eribulin mesylate and pembrolizumab combination treatment will be assessed.

6.5 Pharmacokinetic, Pharmacodynamic and Pharmacogenomic Analysis

6.5.1 Pharmacokinetic Analyses

Plasma concentration versus time data will be analyzed using a population PK approach to estimate population PK parameters. Scatter plots of dose normalized plasma concentration and associated tabulations will be generated by actual sample collection time and for each PK sample collection visit. A separate Population PK data analysis plan will be developed that will describe selection of

appropriate PK structural model, estimation of model parameters and related variability, covariate testing on model parameters as appropriate.

Individual eribulin PK parameters for phase 1b will be, but not limited to $t_{1/2}$, t_{max} , C_{max} , $AUC_{(0-t)}$, t_{last} , $AUC_{(0-inf)}$, , CL, V_z will be calculated based on Cycle 1 Day 1 (C1D1).

6.5.2 Pharmacodynamic Analyses

The effect of soluble biomarkers will be summarized. The analyses will be detailed in a separate analysis plan.

6.5.3 Pharmacokinetic / Pharmacodynamic Analyses

Exploratory/graphical analyses will be conducted for PK/PD evaluations with data from Phase 1b and Phase 2, and be followed by model based analyses. These analyses will be detailed in a separate data analysis plan to be handled by Modeling&Simulation group.

6.5.4 Pharmacogenomic and Biomarker Analyses

Pharmacogenomic and biomarker analyses will be performed and reported separately. Details of these analyses will be described in a separate analysis plan.

6.6 Safety Analyses

All safety analyses will be performed in the Safety Analysis Set. The incidence of treatment-emergent adverse events ([TEAEs, Section 6.6.3](#)) and SAEs will be summarized. Laboratory test results, vital signs and their changes from baseline will be summarized using descriptive statistics (e.g., n, mean, standard deviation, median, Q1, Q3, minimum, and maximum for continuous variables; and n [%] for categorical variables. Abnormal values will be flagged.

Safety information will be summarized by stratum and combined.

6.6.1 RP2D and Dose-limiting Toxicity in Phase1b

The Phase 1b study will include at least 1 safety run-in cohort in which 6 mTNBC subjects who receive eribulin mesylate 1.4 mg/m^2 on Days 1 and 8 and pembrolizumab 200 mg on Day 1 of a 21-day cycle (dose level 1). Subjects will be observed for dose-limiting toxicity (DLT) in the first cycle. The purpose of the safety run-in cohort(s) is to study safety of the 2-drug combination. The Phase 2 part will proceed with dose level 1 when no more than 1 subject has a DLT. Otherwise, a lower eribulin mesylate dose of 1.1 mg/m^2 and pembrolizumab 200 mg will be evaluated in another cohort of 6 subjects. If no more than 1 subject has a DLT in the first cycle, the Phase 2 part will proceed with dose level 0 as the RP2D. Otherwise, alternative doses (eribulin mesylate 0.7 mg/m^2) will be explored prior to the start of the Phase 2 part.

6.6.2 Extent of Exposure

The number of cycles/dose taken on treatment, the number of subjects requiring dose reductions, dose delays, and dose omissions(dose omission were determined by number of study drug not administered as pre-specified from the study drug exposure CRF) for eribulin, and the number of administration of pembrolizumab will be summarized. One cycle is defined as 21 days of treatment. Specifically:

- The number of cycles received and the number of doses taken will be summarized for eribulin with descriptive statistics. Subject is considered received one cycle if the subject received at least one doses on either day 1 or day 8 of a cycle. Also the number of administration of pembrolizumab will be summarized with descriptive statistics.
- The duration of treatment (weeks) by each study drug and overall will be summarized with descriptive statistics. It will be calculated as (date of last infusion with administrated positive dose – date of first infusion + 1)/7 for each drug. It will be calculated as (date of last infusion with administrated positive dose of study drugs – date of first infusion of study drugs + 1)/7 for overall.
- For eribulin, the number of subjects with dose reductions, dose omissions and dose delays will be summarized by counts and percentages according to study medication data. In addition, frequency of dose reductions, dose omissions and dose delays will be summarized by categories (0, 1, and ≥ 2).
- Total dose of eribulin (two definitions: mg and mg/m^2) per subject will be computed as the sum of all of the doses received during study.
- Average dose intensity per subject ($\text{mg}/\text{m}^2/\text{week}$ for eribulin) and relative dose intensity per subject (percent of total dose received relative to total planned dose (including the missed doses)) will be summarized by descriptive statistics for eribulin.

Average dose intensity ($\text{mg}/\text{m}^2/\text{week}$) for eribulin = total dose (mg/m^2)/ duration of treatment in weeks.

Relative dose intensity (RDI)(%) for eribulin= total dose (mg/m^2)/ total planned dose(mg/m^2).

Total dose (mg/m^2), average dose intensity and relative dose intensity will be calculate based on BSA at each visit. If BSA is missing, the last BSA before missing will be carried forward as the BSA for the visit.

Subject data listings will be provided for all dosing records, and for the summary statistics calculated above.

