Pembrolizumab and eribulin mesylate must be administered on Day 1 of each 21-day cycle; pembrolizumab will be given first and followed immediately by eribulin mesylate.

Eribulin mesylate alone will be administered on Day 8 of each 21-day cycle.

Pembrolizumab and eribulin mesylate may be administered up to 3 days before or after the scheduled Day 1 of each 21-day cycle due to administrative reasons. Correspondingly, eribulin mesylate alone may be administered up to 2 days before or after the scheduled Day 8 of each 21-day cycle due to administrative reasons.

Subjects initially treated with eribulin mesylate and pembrolizumab can remain on 1 or both study drugs in the presence of clinical benefit until intercurrent illness, unacceptable toxicity, or disease progression occurs, or until the subject withdraws consent.

For subjects experiencing prolonged clinical benefit, temporary interruption (up to 3 months) of study treatment may be permitted after discussion with the treating physician and the sponsor. After such interruption, investigators are strongly encouraged to rescan the subject to rule out interim progression of disease. In the event of an AE leading to treatment interruption or delay of either study drug, the subject may continue treatment with the other study drug, as long as there is a clinical benefit.

After the last subject has completed 35 cycles of pembrolizumab, all ongoing subjects will be transitioned off study. Subjects still receiving eribulin monotherapy at this time may continue to receive eribulin treatment off study through their pharmacy (if commercially available for that individual subject) or through a patient assistance program administered by the sponsor. Subjects should continue to receive eribulin investigational product and be assessed according to the Schedule of Procedures/Assessments ([Table 8](#)) until they complete the End-of-Treatment visit, prior to their transition to commercial eribulin or an access program.

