9.4.1.1 Eribulin Mesylate Dose Modification During Treatment

Eribulin mesylate dose may need to be delayed and reduced during the study. Dose interruption and dose reduction instructions for subjects who experience eribulin mesylate toxicity are presented in [Table 3](#).

Recommended dose delays:

- Do not administer eribulin mesylate on Day 1 or Day 8 for any of the following:

- Absolute neutrophil count (ANC) <1,000/mm³
- Platelets <75,000/mm³
- Grade 3 or 4 nonhematological toxicities
- Eribulin mesylate Day 8 dose may be delayed for a maximum of 1 week.
 - If toxicities do not resolve or improve to ≤ Grade 2 severity by Day 15, omit the dose.
 - If toxicities resolve or improve to ≤ Grade 2 severity by Day 15, administer eribulin mesylate at a reduced dose and initiate the next cycle no sooner than 2 weeks later.

Recommended dose reductions:

If a dose has been delayed for toxicity and toxicities have recovered to Grade 2 severity or less, resume eribulin mesylate at a reduced dose as set out in Table 3.

Do not re-escalate the mesylate eribulin dose after it has been reduced.

Table 3 Eribulin Mesylate Dose Adjustments for Toxicity

Adverse Reaction / Toxicity ^a	Eribulin Mesylate Dose Modification
Permanently reduce the 1.4 mg/m ² eribulin mesylate dose for any of the following: ANC <500/mm ³ for >7 days ANC <1,000/mm ³ with fever or infection Platelets <25,000/mm ³ Platelets <50,000/mm ³ requiring transfusion Non-hematologic Grade 3 or 4 toxicities Omission or delay of Day 8 eribulin mesylate dose in previous cycle for toxicity	1.1 mg/m ²
Occurrence of any event requiring permanent dose reduction while receiving 1.1 mg/m²	0.7 mg/m ²
Occurrence of any event requiring permanent dose reduction while receiving 0.7 mg/m²	Discontinue eribulin mesylate
If unable to administer a scheduled dose of eribulin mesylate for more than 21 days of study, discuss with sponsor prior to continuing treatment	

ANC = absolute neutrophil count.

a: Toxicities graded in accordance with National Cancer Institute Common Terminology Criteria for Adverse Events, Version 4.03 (NCI-CTCAE, v 4.03).

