9.7.1.8.1 EXTENT OF EXPOSURE

The number of cycles/duration on treatment, quantity of study treatment administered, dose intensity (ie, mg/m²/week for eribulin mesylate) and the number of subjects requiring dose reductions, dose omission, and dose delay will be summarized for eribulin mesylate. The number of administrations of pembrolizumab will be summarized.

Relative dose intensity (RDI) for each study drug will be calculated as D_{ea}/D_{ep} , where D_{ea} is the actual total dose received and D_{ep} is the total planned dose. D_{ep} of eribulin mesylate is calculated based on a subject's body surface area (BSA).

The duration of exposure for each study drug in days is defined as the date of the last dose – the date of the first dose +1. Average cycle length is defined as the duration of exposure divided by the number of cycles in the study.

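### SAP 6.6.2 leaves the rest of the last cycle out of the eribulin dose-intensity divisor, so on-plan dosing reads 26% high after 3 cycles and 7% high after 9

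*SAP*

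**What the plan says.** SAP 6.6.2 defines average dose intensity for eribulin (mg/m²/week) as total dose in mg/m² divided by "duration of treatment in weeks". Duration per drug is the date of the last infusion with a positive dose minus "date of first infusion + 1)/7 for each drug". An overall duration across both drugs is also defined, and the dose-intensity formula does not say which of the two it uses. The section adds: "One cycle is defined as 21 days of treatment".

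Relative dose intensity (RDI) is a separate measure, described as "percent of total dose received relative to total planned dose (including the missed doses"; it has no duration term.

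Protocol 9.7.1.8.1 uses the same span: "The duration of exposure for each study drug in days is defined as the date of the last dose", less the first dose date, plus 1. It gives dose intensity only as mg/m²/week and names no divisor.

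On dosing, Protocol 9.4.1 gives both drugs on Day 1 and then states: "Eribulin mesylate alone will be administered on Day 8 of each 21-day cycle". Neither document adds the days after the last dose back into the dose-intensity divisor.

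**The concern.** Last-minus-first-plus-1 is a reasonable description of how long a subject was treated. It is not the time over which the doses were spread, because each pair of eribulin doses is meant to cover 21 days. Used as a divisor, it credits the last cycle with its full dose but only 8 of its 21 days.

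The bias always runs upward and is largest in subjects who stop early. In short courses the row can show a subject above plan whose dose was reduced or whose last Day 8 was omitted. Because it depends on course length, it also disturbs comparison between groups. SAP 6.6 summarises safety information by stratum, so if the strata differ in treatment length (an assumption), identical on-plan dosing would give different averages.

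**Working it through.** The documents state no dose-intensity figure, so there is nothing to reproduce. The check applies the SAP formula to a subject dosed on plan.

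**Inputs.** 1.4 mg/m² on Days 1 and 8 of a 21-day cycle (Protocol Table 2); cycle length and duration formula (SAP 6.6.2).

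**Planned rate.** 2 × 1.4 / 3 weeks = 0.933 mg/m²/week.

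**SAP value after k on-plan cycles ending on Day 8.** Total dose is 2.8k. Duration is 21(k − 1) + 8 = 21k − 13 days. Average dose intensity is 2.8k × 7 / (21k − 13), which is 21k / (21k − 13) times plan.

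| Cycles | Dose (mg/m²) | Days counted | SAP value | Against 0.933 |
|---|---|---|---|---|
| 1 | 2.8 | 8 | 2.45 | +163% |
| 3 | 8.4 | 50 | 1.18 | +26% |
| 4 | 11.2 | 71 | 1.10 | +18% |
| 9 | 25.2 | 176 | 1.00 | +7% |
| 35 | 98.0 | 722 | 0.95 | +2% |

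Moving the last Day 8 dose within its 2-day administrative window changes the 3-cycle excess to between 21% and 31%, and the 9-cycle excess to between 6% and 9%.

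**Which rows matter.** The first scheduled on-treatment scan, at week 9, falls at 63/21 = 3 cycles. The eribulin median PFS values in Protocol Table 1, 67 and 87 days, are 3.2 and 4.1 cycles, but they come from other trials of eribulin alone. The Synopsis expects a median treatment duration of 6 months: 182.6/21 = 8.7, taken as 9 cycles.

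**Dose reduction.** Three on-time cycles, with cycles 2 and 3 at 1.1 mg/m² (the first reduced level in Protocol Table 3): total 2.8 + 2.2 + 2.2 = 7.2.
- SAP value: 7.2 × 7/50 = 1.008, above plan.
- Over three full cycles: 7.2/9 = 0.80.
- RDI: 7.2/8.4 = 86%.

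**Last dose on Day 1.** Three cycles with the final Day 8 omitted: 7.0 × 7/43 = 1.14, against 7.0/9 = 0.78 over full cycles.

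**Cross-check.** Protocol 9.7.1.8.1 defines average cycle length as the same duration divided by the number of cycles. Three exact 21-day cycles would then average 50/3 = 16.7 days.

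**Check of the remedy.** On plan, Day 1 of the last cycle plus 21 days, minus the first infusion date, is 21k days, or 3k weeks. Then 2.8k/3k = 0.933 for every k.

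**The case against.** The best defence is that this is a definition, stated consistently in protocol and SAP, for one descriptive row in a single-arm study. No document compares the result with 0.933. Delays, omissions and reductions are tabulated separately, and all dosing records and derived statistics are listed, so a reader could recompute the rate. At the expected 6-month duration the excess is about 7%. All of that stands, and it keeps the point minor. It does not make the ratio right: no finite course dosed exactly on plan returns the planned rate.

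A reader might go further and infer that RDI cannot see delays, so that average dose intensity is the only measure that could and it fails. The documents do not support that. They do not say whether total planned dose is counted per cycle started or on a 21-day calendar. Take three full-dose cycles spaced 28 days apart, with the last dose on study Day 64. Counted per cycle, RDI is 6/6 = 100%. On a 21-day calendar seven doses are due by then (Days 1, 8, 22, 29, 43, 50 and 64), and RDI is 6/7 = 86%. Nor is that pattern what the toxicity rules produce: Protocol 9.4.1.1 resumes eribulin at a reduced dose after a toxicity delay, and 9.4.1 allows only 3 days either side of Day 1 for administrative reasons.

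A fair objection to any repair is that the end of the last cycle is not observed. Adding 21 days for everyone would penalise a subject cut off mid-cycle. An on-plan subject with data cut at Cycle 3 Day 1 has 5 doses and would read 7.0/9 = 0.778, 17% below plan with no dose missed. The fix has to deal with that.

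**Conclusion.** The formula is wrong as written, and the point is minor. Eribulin average dose intensity is overstated by a factor of 21k/(21k − 13) for on-plan dosing that ends on Day 8: 26% at 3 cycles, 18% at 4 and 7% at 9. In short courses it can place a dose-reduced subject above plan.

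These figures assume 21-day cycles, doses on the scheduled days and the eribulin-specific duration as divisor. The effect is confined to this one row. It does not reach ORR, the RP2D, RDI, the counts of delays, omissions and reductions, or the listings. Whether RDI reflects delays is left open by the documents and is no part of this conclusion.

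**What to change.** In SAP 6.6.2, for average dose intensity only:

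- State that the eribulin-specific duration applies, and set the divisor to (Day 1 of the last eribulin cycle + 21 days − date of first eribulin infusion)/7.
- If the last cycle is still in progress at data cutoff, leave it out of both numerator and divisor. The subject cut off at Cycle 3 Day 1 then reads 5.6/6 = 0.933.
- Footnote that the last cycle counts as 21 days by convention, including for subjects who stop or die within it or whose last Day 8 dose was delayed.
- Keep last-minus-first-plus-1 for the duration-of-treatment row.

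The cost is one formula, one cutoff rule and one footnote; Protocol 9.7.5 already provides for recording deviations from the protocol's analysis plan in the SAP. Reported dose intensity will be somewhat lower, most in short courses. A subject whose only eribulin cycle is in progress at cutoff will have no value. The 21 days remain a convention: under Protocol 9.4.1.1 a Day 8 dose can be delayed by up to a week, with the next cycle no sooner than 2 weeks after it, so such a cycle may in fact run longer. The case report form is not among the documents, so the sponsor should confirm that a Day 1 date is held for any last cycle in which only the Day 8 dose was given.
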